In a study involving 21 perimenopausal women with vulvovaginal atrophy, Arroyo et al. treated women with fractional CO₂ laser over a series of 3 treatments and then reevaluated symptoms and tissue 12 and 24 weeks later via vaginal health index (VHI) scores.¹ At 12 weeks, 82% of patients had significant improvement in VHI. Additionally, 97% of patients reported no to mild discomfort with treatment. Itching was the most commonly reported side effect (20%).

Lee et al. used ablative CO₂ laser and fractional CO₂ laser therapy on five patients with hyperkeratotic vulvar lichen sclerosus that was previously unresponsive to topical steroids. This study included five women with vulvar lichen sclerosus recalcitrant to topical treatment with clobetasol propionate 0.5% ointment as evidence by ongoing symptoms and gross physical exam. Of the 4 women who reported symptoms before treatment, 100% experienced improvement after CO₂ laser treatment. Coyle also used laser therapy via the ProFractional Er:YAG Fractional Ablative Laser (Sciton, Inc.). This study is unique in that pretreatment biopsies were used to determine depth of vulvar lichen sclerosus. Using this histologically determined depth, the investigator individualized depth of laser treatment to match over 3 laser treatment sessions. A total of 15 patients were enrolled, and at 3 months, a repeat biopsy showed 7 participants (58.3%) had no vulvar lichen sclerosus with 41.6% of participants reporting improvement in symptoms compared to baseline. Peterson et al. also had successful results in two patients using CO₂ laser therapy with a treatment protocol that involved two passes of the CO₂ laser or until there was no evidence of disease present.⁸

Another consideration related to laser therapy is long-term results. Windahl et al. evaluated 62 male patients who had histologically proven lichen sclerosus and treated with CO₂ laser therapy. Of the 62 men evaluated, 50 were available to interview and 80% reported no recurrence of symptoms; median follow-up was 14 years.

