Prior to receiving treatment, topical anesthetic will be applied to the affected area for 20-30 minutes and then wiped away. The treatment area will be cleaned and dried of any moisture prior to treatment. The disinfected standoff with sapphire plate will then be applied to the ProFractional hand piece. Based on the biopsy results, the appropriate ablation depth will be inputted with 11% treatment density selected. Each treatment will include two passes of the laser over the affected area.

- Visit 1, month 0: On the first pass, the depth of the laser will be from 300 to 500 microns, or the thickness of 3 to 5 sheets of paper; the depth will be based on the biopsy that was used to diagnosis the lichen sclerosus. On the second pass, the depth will be 50 microns deeper than the first pass and the hand piece rotated 45°.
- Visit 2, month 1: The first pass of the laser will be the same depth as the second pass from the last visit. The second pass will be 50 microns deeper and the hand piece rotated 45°.
- Visit 3, month 2: The first pass of the laser will be the same depth as the second pass from the last visit. The second pass will be 50 microns deeper and the hand piece rotated 45°.

Participants will return for follow-up visits at 1 and 3 months (months 3 and 5 of the study) following the third treatment.

- Visit 4. month 3
 - o Participants will be asked to complete questionnaires to assess outcomes.
- Visit 5. month 5
 - Participants will be asked to complete questionnaires to assess outcomes.
 - We will take photographs of the affected area.
 - Biopsy of area with lichen sclerosus; the biopsy will be done the same way as the one that was done to diagnosis your lichen sclerosus

If participants prefer not to come in person for Visit 4 due to concerns over COVID-19, they may have a telehealth visit instead to check in with their provider. In that case, the participant would complete the Visit 4 survey remotely, either over the phone with the study coordinator or online via REDCap.

Outcome Assessment

The primary outcomes will be change in histology and depth of disease from baseline to three months

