after the last laser treatment. The baseline depth of lichen sclerosus will be based on the results of the clinical biopsy performed before study participation. We will use the study biopsy collected at the follow-up visit three months after the last treatment to determine resolution of disease or, if disease persists, to what depth. The biopsies will therefore serve as an objective means to determine effective treatment of disease.

The secondary outcomes will include the following:

- Change in symptoms and quality of life using the Vulvovaginal Symptom Questionnaire
- Change in symptom severity using the Patient Global Impression scales for severity and improvement
- Vulvar lichen sclerosus improvement as assessed using photographs. Photographs will be rated by observers blinded to whether a photo is before or after treatment.
- Satisfaction with treatment using a participant satisfaction questionnaire

B. Statistical Considerations

Sample size

Based on the limited prior data, we anticipate that 60% of participants will achieve the primary outcome, which is resolution of lichen sclerosus on biopsy at three months after completion of treatment. Using a one-sample binomial proportion test and assuming a two-sided alpha=0.05 and power=85%, we would need to 27 evaluable participants to show that 60% is statistically different from a reference proportion of 30%. To account for 10% potential loss to follow-up, we aim to enroll 30 participants.

Statistical Analysis

We will present data as mean (± standard deviation), median (interquartile range), or proportion, based on data type and distribution. Continuous data will be compared with the appropriate parametric or non-parametric test, accounting for paired data as needed. Categorical data will be compared with the chi-square, Fisher's exact, or McNemar's test. P values <0.05 will be considered statistically significant. Analyses will be conducted with SAS 9.4 (SAS Institute, Cary, North Carolina).

PI Revision Date: 10.29.2020

C. Participant Selection

Inclusion criteria

- Female
- Aged 18 years old or older
- · Biopsy-proven active vulvar lichen sclerosus
- Characteristic changes of vulvar lichen sclerosus on gynecological exam
- Self-reported indication of one or more of the following symptoms of lichen sclerosus
 - o Dryness
 - Itching
 - Burning
 - Bleeding
 - Blistering
 - Soreness
 - Easily bruises
 - Easily tears
 - Ulcerated lesions
 - Painful intercourse

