- Ability to complete questionnaires in English
- Written, informed consent
- Willing and able to logistically follow schedule of treatments and follow-up visits

Exclusion criteria

- Receiving systemic immunosuppressant's (e.g. corticosteroids) within 4 weeks of enrollment
- Use of topical vulvar steroid-containing creams at the affected area within 4 weeks of enrollment
- Immunocompromised (e.g. lymphoma, AIDS, Wiskott-Aldrich syndrome)
- · History of uncontrolled malignant disease
- · Additional genital skin disease
- Known allergy or intolerance to topical anesthesia
- Known history of connective tissue disease
- Known propensity for keloid formations

B4. POSSIBLE BENEFITS

It is possible that participants may benefit from an improvement in their vulvar lichen sclerosus symptoms and quality of life. Patients with vulvar lichen sclerosus and their providers will benefit from the increased clarity on the effectiveness of laser treatments, potentially expanding the now limited treatment options available to those who are ineligible for high potent topical steroids or have failed topical treatment.

PI Revision Date: 10.29.2020

B5. POSSIBLE RISKS AND ANALYSIS OF RISK/BENEFIT RATIO

This study poses minimal risks to participants. As shown in a peer-reviewed study where the fractional Er:YAG laser was used to improve postsurgical facial scars from skin cancer surgery, adverse effects were limited to transient hyperpigmentation and erythema. ¹² The treatments will be carried out by skilled and trained providers. Any discomfort caused by the laser treatments themselves will be attempted to be mitigated by the application of topical anesthetic prior to treatments.

Other than potential discomfort from the laser, other risks include vulvar spotting (light bleeding), allergic reaction to topical anesthetic, and infection from the biopsy or the laser treatment

The only other foreseeable risk is that associated with participant confidentiality. To protect participant privacy, all data will be handled in a confidential manner. All electronic data will be kept in a password-protected folder on the BIDMC secure server behind the firewall or in REDCap. Any paper associated with the study will be kept in a locked office.

Risks associated with this study are minimal. Given the possible benefits both for participants themselves and scientific knowledge gained, the benefits are believed to outweigh the risks.

B6. RECRUITMENT AND CONSENT PROCEDURES

Recruitment

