We will attempt to identify and recruit study participants at a clinical visit with gynecology, gynecologic oncology, radiation oncology, or surgical oncology. We will also post flyers at these clinics in order to inform potential participants about this study.

Consent

Written, informed consent will be obtained by members of the study team from participants prior to the collection of any data. Informed consent will occur in a private area; study staff will be able to answer any questions from potential participants. Potential study participants will be clearly informed that it is unclear whether fractional 29240 nm laser therapy is beneficial for symptoms of lichen sclerosus.

Participant Protection

All potential participants will be informed that participation in the study will in no way affect their clinical care. Written, informed consent will be obtained from all participants, and participants will be informed that they can withdraw from the study at any point.

B7. STUDY LOCATION

Privacy

All consent and data collection will be conducted in a private setting. The information being collected is limited to only the minimum amount of data necessary to accomplish our objectives.

Physical Setting

We have a dedicated procedure room where all laser treatments will be performed.

PI Revision Date: 10.29.2020

| D | D 4 : | T A C | | IDITY |
|-----|-------|-------|-----|-------|
| B8. | DA | IAS | ヒしい | IRITY |

| All electronic data will be kept in a restricted-access folder on the BIDMC secure server, behind the firewall or in REDCap. Any paper resulting from this study will be kept in a locked office belonging to a member of the study staff. | | | |
|--|--|--|--|
| B9 Multi-Site Studies | | | |
| Is the BIDMC the coordinating site? | | | |
| Is the BIDMC PI the lead investigator of the multi-site study? | | | |
| | | | |
| B10 Dissemination of Research Results | | | |
| We plan to present the data at national and international meetings and publish the results in a peer-reviewed journal. Data will be reported only in aggregate. | | | |
| | | | |

References

- 1. Arroyo C. Fractional CO(2) laser treatment for vulvovaginal atrophy symptoms and vaginal rejuvenation in perimenopausal women. Int J Womens Health. 2017 Aug 28;9:591-595. doi: 10.2147/IJWH.S136857. eCollection 2017.

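### Is a 10% allowance for loss too small, given that the plan's own prior repeat-biopsy study seems to have no result for 3 of 15 patients?

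*Combined protocol and SAP*

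**What the plan says.** Section B3.B (Sample size) sets the target on a one-sample binomial proportion test, two-sided alpha 0.05 and 85% power: "we would need to 27 evaluable participants to show that 60% is statistically different from a reference proportion of 30" per cent. The response rate is introduced with "Based on the limited prior data, we anticipate that 60% of participants will achieve the primary outcome", that outcome being resolution on biopsy three months after treatment ends. Enrolment then follows: "To account for 10% potential loss to follow-up, we aim to enroll 30 participants". No basis is given for the 10%.

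The outcome depends on the study biopsy at Visit 5 (B3.A). Section B2 summarises one earlier study of the ProFractional Er:YAG laser in this disease, in which the investigator "individualized depth of laser treatment to match over 3 laser treatment sessions". Its result is given as "A total of 15 patients were enrolled, and at 3 months, a repeat biopsy showed 7 participants (58.3%) had no vulvar lichen sclerosus".

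Three other statements bear on attendance:
- B3.A, for Visit 4 only: "If participants prefer not to come in person for Visit 4 due to concerns over COVID-19, they may have a telehealth visit instead".
- B3.C, as an inclusion criterion: "Willing and able to logistically follow schedule of treatments and follow-up visits".
- B6: "participants will be informed that they can withdraw from the study at any point".

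**The concern.** The earlier study is the closest precedent in the document: same device, three sessions, biopsy at three months. Its 58.3% cannot be 7 of 15, which is 46.7%. It must be 7 of 12, so three enrolled patients appear to have no repeat-biopsy result. The plan's anticipated 60% is close to the rate among those 12, yet its allowance for missing results is half of what the same study implies. The plan would then be taking the favourable half of its evidence and leaving the unfavourable half.

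Two features seem to point the same way. A participant can attend Visit 5 and still have no readable biopsy, which the phrase loss to follow-up does not obviously cover. And the remote option exists for Visit 4 only, whereas the biopsy has to be taken in person.

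At stake is power for the primary outcome. A single-arm study of 30 has little to spare, and a non-significant result from an underpowered one is hard to interpret.

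**Working it through.** **Inputs.** From B3.B: reference proportion 0.30, anticipated proportion 0.60, two-sided alpha 0.05, power 85%, 27 evaluable, 10% loss, 30 enrolled. From B2: 15 enrolled, 7 clear, reported as 58.3%; 41.6% with symptom improvement.

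**1. Reproduce the plan's figures.** Take the exact binomial test with 0.025 in each tail. For n evaluable, find the smallest r with P(X ≥ r | n, 0.30) ≤ 0.025. Power is then P(X ≥ r | n, 0.60); the lower tail adds nothing material.

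| Evaluable n | Critical r | Upper-tail alpha | Power |
|---|---|---|---|
| 23 | 12 | 0.0214 | 83.6% |
| 24 | 13 | 0.0115 | 78.7% |
| 25 | 13 | 0.0175 | 84.6% |
| 26 | 14 | 0.0094 | 80.1% |
| 27 | 14 | 0.0143 | 85.5% |

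27 is the smallest n that reaches 85%, and 27/0.90 = 30. Both stated figures reproduce. Other versions of the test need different numbers for 85% (normal approximation 22, arcsine 24, continuity-corrected 26), so the equal-tailed exact test is the natural yardstick.

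**2. The implied loss in the earlier study.** 7/11 = 63.6%, 7/12 = 58.3%, 7/13 = 53.8%, 7/15 = 46.7%. Only 12 fits. The second percentage agrees: 5/12 = 41.7%. So 15 − 12 = 3, and 3/15 = 20%. This is inferred from arithmetic; the text does not state it and gives no reason.

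**3. How much 3 of 15 says about 10%.** The exact (Clopper-Pearson) 95% interval is 4.3% to 48.1%. If the true loss were 10%, three or more missing of 15 would occur with probability 0.184. The 10% is therefore not contradicted.

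**4. Effect of 20% loss, taken at one n.** 30 × 0.80 = 24 evaluable, power 78.7%. The chance of missing a true 60% rises from 14.5% to 21.3%, a ratio of 21.3/14.5 = 1.47. But the table shows that 24 is a low point: losing one more participant raises power to 83.6%. Part of the apparent drop is discreteness.

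**5. Effect averaged over random loss.** Let the number evaluable be binomial with size N and probability 1 − loss, and average the exact power over it.

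| Loss | N = 30 | N = 34 |
|---|---|---|
| 10% | 85.3% | 90.6% |
| 15% | 82.9% | 88.3% |
| 20% | 80.5% | 85.6% |

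On this measure the chance of missing the effect with 30 enrolled goes from 14.7% to 19.5%, a ratio of 19.5/14.7 = 1.33. The chance of having at least 27 evaluable from 30 falls from 64.7% at 10% loss to 12.3% at 20%.

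**6. What a larger enrolment would buy.** 27/0.80 = 33.75, so 34. That is four more participants (4/30 = 13%) for 85.6 − 80.5 = 5.1 points of averaged power if loss is 20%. If loss is 10%, the 85% target is already met without them.

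**The case for a change.** The best case for acting is that the plan uses its evidence unevenly. It adopts a response rate close to the one seen among biopsied patients and does not carry over the missing biopsies from the same study. The shortfall survives averaging, so discreteness does not explain all of it. Four missing biopsies are enough to fall below 27, and at 20% loss the chance of reaching 27 is only about one in eight. Four more participants would restore the target. Failing that, a sentence justifying 10% and giving the power at higher loss would cost almost nothing.

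What stands is that 10% is unsupported in the text and optimistic against its only close precedent. The rest carries less weight:
- The cause of the three missing results is unknown. They may have been untreated, not yet at three months, or lost, and only some of these would carry over to this trial. The link between the 60% and that study is also an inference, since the plan credits only limited prior data.
- The COVID-19 provision is conditional and concerns Visit 4. Anyone due at Visit 5 will normally have come in person for three laser sessions, and entry requires being willing and able to keep the schedule. The right to withdraw is standard and says nothing about the rate.
- The distinction between lost and not evaluable is mostly wording, because the plan counts evaluable participants and inflates from that number.
- The Statistical Analysis paragraph does not repeat the primary test or name an analysis set. The sample-size paragraph already supplies the one-sample binomial test and the evaluable participants, so an analyst can fill that gap sensibly. It is in any case separate from the enrolment number.

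**Conclusion.** No change is needed. At its stated 10% allowance, 30 enrolled gives 27 evaluable and 85.5% exact power, so the plan delivers what it claims. The alternative of 20% rests on an inferred 3 of 15, with a 95% interval of 4.3% to 48.1% and no known cause; it raises a fair question about the allowance without showing it to be wrong. If 20% did occur, averaged power would be about 80.5% (82.9% at 15%), and the 78.7% at exactly 24 overstates the fall. Enrolling 34 would exchange one uncertain allowance for another, at the cost of four more people each having three laser sessions and a biopsy, when no stated figure is missed. Documenting a basis for 10% would be good practice but would alter no number and no analysis.

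This rests on the equal-tailed exact test being the one behind the plan's 27, on analysis of participants with an evaluable Visit 5 biopsy, and on missing biopsies being unrelated to whether disease has resolved.

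### Does the Statistical Analysis paragraph drop the one-sample test against 30% on which the trial is sized?

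*Combined protocol and SAP*

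**What the plan says.** Section B3.B, Statistical Considerations, has two short paragraphs.

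- **Sample size** identifies "the primary outcome, which is resolution of lichen sclerosus on biopsy at three months after completion of treatment". It then states the test and error rates, "Using a one-sample binomial proportion test and assuming a two-sided alpha=0.05 and power=85" per cent, and the aim, to "show that 60% is statistically different from a reference proportion of 30" per cent. The result is 27 evaluable participants, and then "To account for 10% potential loss to follow-up, we aim to enroll 30 participants".
- **Statistical Analysis** gives general rules for all data: "Continuous data will be compared with the appropriate parametric or non-parametric test, accounting for paired data as needed", and "Categorical data will be compared with the chi-square, Fisher's exact, or McNemar's test". Significance is set at P below 0.05. No test is tied to a named outcome.

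Outcome Assessment, in B3.A, lists change in histology and depth of disease together as primary outcomes, and says the follow-up biopsy is used "to determine resolution of disease or, if disease persists, to what depth". Every participant enters with disease on biopsy, under the criterion "Biopsy-proven active vulvar lichen sclerosus".

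**The concern.** The trial has no comparison arm, so the 30% reference is the only benchmark against which resolution can be judged. The analysis paragraph mentions neither that benchmark nor a one-sample test, and the three tests it lists fit the primary outcome poorly:

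- Fisher's exact test needs a second group, which the design does not have.
- Chi-square works only as a goodness-of-fit test against 30%, which the paragraph does not say.
- McNemar's test compares before with after. Nobody is resolved at baseline, so it would test resolution against 0%.

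If an analyst took the list as complete, the trial could be declared positive at a count that fails the test it was sized on. With McNemar's test this could happen at a resolution rate below 30%. The status of depth, co-primary or supportive, is also not spelled out.

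**Working it through.** **Inputs** (Sample size paragraph, B3.B): reference proportion 0.30, anticipated proportion 0.60, two-sided alpha 0.05, power 85%, 27 evaluable, 10% loss, 30 enrolled.

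**1. Reproducing the plan's figure.** Let X be the number resolved, binomial with n = 27. Use an exact test with at most 0.025 in each tail.

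- Upper tail under 0.30: P(X ≥ 13) = 0.0359, too large; P(X ≥ 14) = 0.0143, acceptable.
- Lower tail under 0.30: P(X ≤ 3) = 0.0202.
- True two-sided size: 0.0143 + 0.0202 = 0.0344 before rounding of the parts, or 3.4%.
- Power at 0.60: P(X ≥ 14) = 0.855.
- Power is 84.6% at n = 25 and 80.1% at n = 26, and 27 is the first n from 10 upwards to reach 85%.
- Enrolment: 27 / 0.90 = 30.

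Both stated figures reproduce. The 27 also helps to identify the intended test. Other versions first reach 85% at different sizes: minimum-likelihood exact 24, uncorrected chi-square 22, continuity-corrected 26, Wald 26.

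**2. Versions of the one-sample test against 30% at n = 27.** The expected count is 27 × 0.30 = 8.1, with standard deviation √(27 × 0.30 × 0.70) = √5.67 = 2.381.

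| Version | p at 13/27 | Responders needed | Power at 60% |
|---|---|---|---|
| Exact, doubled tail | 2 × 0.0359 = 0.072 | 14 | 85.5% |
| Exact, minimum likelihood | 0.056 | 14 | 85.5% |
| Chi-square, continuity-corrected | z = (4.9 − 0.5)/2.381 = 1.85; 0.065 | 14 | 85.5% |
| Wald | 0.059 | 14 | 85.5% |
| Chi-square, uncorrected | z = 4.9/2.381 = 2.06; 0.040 | 13 | 92.6% |

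On the side that shows benefit, 13 of 27 is the only count where the versions disagree. P(X = 13) is 0.022 at a true 30% and 0.070 at a true 60%. The uncorrected chi-square has true size 5.6% at n = 27, against 3.4% for the exact rule.

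**3. Other evaluable counts.** Responders needed at n = 25, 26, 27, 28, 29, 30:

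- doubled-tail exact: 13, 14, 14, 14, 15, 15;
- minimum-likelihood exact: 13, 13, 14, 14, 14, 15;
- uncorrected chi-square: 12, 13, 13, 14, 14, 14.

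The versions never differ by more than one responder. The uncorrected chi-square reaches a true size of 7.8% at n = 25 and 7.0% at n = 30.

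**4. McNemar's test, if it were applied to resolution.** With b resolved and none worsening from a resolved state, exact p = 2 × 0.5^b. This is 0.0625 at b = 5 and 0.031 at b = 6, so significance starts at 6/27 = 22%. If true resolution were 30%, P(X ≥ 6) = 0.864. That is a large consequence, but only if the plan sends resolution to McNemar's test, and no sentence in it does.

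**The case for a change.** The strongest contrary argument is that a sizing assumption is not an analysis commitment. The only paragraph headed as analysis lists other tests, and the primary outcome is also worded as a change from baseline, which invites a paired test. Results of 6 to 13 out of 27 fail the sized test but could be called significant under some listed test. Prevention would cost a few sentences and no extra participants.

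Part of this stands. The paragraph does not cross-refer to the sizing test, and a cross-reference would be tidier. The 6-to-13 range does not carry the weight placed on it. Counts 6 to 12 become significant only by testing resolution against 0%, when the paragraph immediately above states 30%. In a study where everyone is diseased at entry, such a test has no useful meaning. McNemar's has an obvious use elsewhere, for dichotomised paired secondary outcomes such as symptoms. Without that reading, only 13 of 27 remains, and only if the uncorrected chi-square is chosen.

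Prescribing a particular exact tail convention would be largely preference: both exact versions have the same rejection region at 27 and differ by one responder at 26 and at 29. The status of depth is a separate question of endpoint definition. The sizing paragraph speaks of one primary outcome, resolution. Outcome Assessment has depth determined where disease persists, and the paired-data rule for continuous outcomes covers its analysis.

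**Conclusion.** The observation is literally correct, but it does not call for a change. Read as one section, B3.B gives the primary outcome, the test, its level and its comparator, and the stated 27 and 30 follow exactly from them. The general list of categorical tests is a default for the remaining outcomes, and an analyst following the whole section would reach a sound primary result.

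The residual ambiguity at the planned size is a single count, 13 of 27, with probability 2.2% at a true 30% and 7.0% at a true 60%, and only under the uncorrected chi-square. At 25 to 30 evaluable the exact versions and the uncorrected chi-square never differ by more than one responder.

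This conclusion assumes that the analyst takes the primary test from the sizing paragraph, as its wording and its reproducible sample size indicate, and that resolution, not depth, carries the primary conclusion. Repeating the test in the analysis paragraph would be harmless, but it would only restate what the section already contains.
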